# 5.4 STUDY DESIGN AND SAMPLE SIZE

Total sample size: 100

The study will be conducted as a randomized comparative effectiveness trial with two arms. Subjects will be randomized to one of two treatments WITH either hyoscyamine or tamsulosin. Our hypothesis is that the hyoscyamine is at least as effective as tamsulosin in treating lower urinary tract symptoms. Symptoms will be quantified using the Urinary Symptom Index (USI) of the validated Ureteral Stent Symptom Questionnaire (USSQ). To address the hypothesis, the study will be conducted as a non-inferiority trial, following the hypothesis that hyoscyamine is not inferior to tamsulosin by more than a 15% margin in terms of the USI. The sample size was estimated using the PowerTOST package for the R statistical environment, based on a nominal power of 80% and an alpha-level of .025 for the one-sided t-test. Our null hypothesis is therefore that the mean USI for those treated with tamsulosin is more than 15% greater than those treated with hyoscyamine, so that by rejecting it, we may conclude hyoscyamine is not-inferior to tamsulosin by more than a 15% margin of USI for treating lower urinary tract symptoms. Furthermore, we assume that the coefficient of variation (CV) for the mean Urinary Index Score

will be similar to that in Park, et al.20 The CV in that study for the Urinary Symptom Index at week 2 after stent placement for the tamsulosin group was approximately .25. This is slightly higher, but similar to the CV of .22 for the USI in Maldonado-Avila, et al. which collected data at week 1, and therefore should be slightly conservative.21 Using these assumptions, we estimated that the sample size for each arm would need to be approximately 47, in order to have the desired power.

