# **5.5 DATA ANALYSIS**

The main hypothesis of the non-inferiority of hyoscyamine to tamsulosin for treating lower urinary tract symptoms will be tested using a t-test for non-inferiority of the change in USI between POD1 and POD7 (or day of stent removal if removed before day 7) in each treatment arm. This should be slightly more powerful than the t-test at POD7 alone that we used to estimate the sample size, but there are not enough data available for the distribution at POD1 in order to make a good estimate of the change. The non-inferiority margin will be 15% of the change in USI. The primary analysis will be conducted as intention-to-treat (ITT). That is, subjects will be analyzed as belonging to the arm they were randomized to, irrespective of later crossover or other modifications. This approach is in line with the current statement on Consolidated Standards of Reporting Trials (CONSORT). Descriptive statistics will be used to describe the results from all USSQ domains at each timepoint (i.e. mean and standard deviation, along with confidence intervals for urinary symptom index, pain symptom index, etc.). We will also conduct non-inferiority tests of change in score for ITT with hyoscyamine versus tamsulosin for the other domains spanned by the USSQ, including pain symptom index, general health index, work performance index, and sexual matters between POD1 and POD7, although we may not be wellpowered to detect non-inferiority for these additional domains.

The secondary goal of determining if there are differences in the amount of additional medications need to treat stent-related discomfort between treatment arms will be examined primarily through descriptive statistics. The drug diaries of all subjects will be used to tabulate the kinds and amounts of additional medications used. For each subject, the number of days that additional medications were used will be counted. The proportion of days that additional medications were used will be calculated for each group and 95% confidence intervals will be calculated.

Finally, we will also calculate the informed consent rate, and the discontinuation rate for those patients needing to be removed from the study in each arm.

In all cases, a p-value  $\leq$  .05 will be taken as a statistically significant result.

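### The non-inferiority margin is only a percentage, with no point value or reference arm, so the planned t-test need not hold the stated one-sided .025, and 80% power at 47 per arm fits only a fixed margin on the POD7 level

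*Combined protocol and SAP*

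**What the plan says.** Section 5.4 frames the trial as non-inferiority, with the hypothesis that "hyoscyamine is not inferior to tamsulosin by more than a 15% margin in terms of the USI". The null is written as a comparison of two means: "the mean USI for those treated with tamsulosin is more than 15% greater than those treated with hyoscyamine". Sizing is "based on a nominal power of 80% and an alpha-level of .025 for the one-sided t-test", using PowerTOST and a CV of about .25 for the USI at week 2 in the tamsulosin arm of a cited trial (.22 at week 1 in a second trial). From this, "we estimated that the sample size for each arm would need to be approximately 47".

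Section 5.5 moves the primary analysis to a different quantity. The hypothesis is "tested using a t-test for non-inferiority of the change in USI between POD1 and POD7", or to stent removal if that comes sooner, and "The non-inferiority margin will be 15% of the change in USI". The same section explains that sizing used the POD7 value alone, because data on POD1 were too sparse to estimate the change.

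Neither section gives the margin in USI points, an expected USI mean, the arm whose mean or change is the base of the 15%, or a ratio method (log scale or Fieller).

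**The concern.** A t-test for non-inferiority compares a difference in means with a constant. A percentage becomes a constant only when it is multiplied by a number fixed beforehand, and the plan supplies none. For the change score it says that no good prior estimate exists. An analyst following section 5.5 would therefore most naturally take 15% of the change seen in the trial.

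That margin varies from sample to sample and is correlated with the arm mean it is taken from. The ordinary standard error ignores both facts, so the test no longer has its nominal error rate. The non-inferiority conclusion depends entirely on the margin. The trial is also open-label, so an unfixed threshold could be settled after results by arm are visible.

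**Working it through.** **Inputs.** From section 5.4: one-sided alpha .025, power 80%, 15% margin, CV .25 (second source .22), 47 per arm, total 100. From section 4.3: completion at 94 completers. Assumed, because the documents do not say: equal true means for the power calculations, equal SDs, 1:1 allocation, and higher USI meaning worse symptoms. USI is scaled so that the tamsulosin mean is 1; the SD is then .25 and the margin .15.

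**1. The plan's figure.** With a fixed margin on the POD7 level, n = 2(1.96 + 0.842)² × (.25/.15)² ≈ 44 per arm; the exact noncentral t gives 45. At 47 per arm, SE = .25 × √(2/47) = .0516 and .15/.0516 = 2.91. Power is 82.1% (exact t). The stated 47 agrees to within two patients. No variant tried at CV .25 gives exactly 47; the log-ratio calculation gives 49 (normal) or 50 (exact t).

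**2. Error rate if the margin is taken from the observed tamsulosin mean.** The statistic compares the hyoscyamine mean with θ times the tamsulosin mean. Its true variance is σ²(1 + θ²)/n, but the t-test uses 2σ²/n. The true one-sided error is therefore about Φ(−1.96/√((1 + θ²)/2)).

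- θ = 1.15: √(2.3225/2) = 1.078; Φ(−1.819) = 3.4%.
- θ = 0.85 (retain 85% of an improvement): √(1.7225/2) = 0.928; Φ(−2.112) = 1.7%.
- Margin fixed in points: 2.5%.

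Simulation of 400,000 trials at 47 per arm gave 3.45%, 1.73% and 2.51%. If the CV rather than the SD is equal across arms, the first two become 3.3% and 1.6%. With equal SDs the result depends only on θ, so it also applies to change scores. Exchanging the arm labels, to match the null as literally written, leaves the 1.15 result unchanged.

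**3. Power of a valid ratio test of the POD7 level.**

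- Log scale: SD = √ln(1 + .25²) = .246, margin ln 1.15 = .140.
- Fieller contrast: SE = .25 × √(2.3225/47) = .0556, and .15/.0556 = 2.70.

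| Test, CV .25 | n for 80% | Power at 47 | Power at 50 |
|---|---|---|---|
| Fixed margin | 45 | 82.1% | 84.4% |
| Log, 1.15 | 50 | 77.7% | 80.2% |
| Fieller, 1.15 | 52 | 76.1% | 78.7% |
| Log, 0.85 | 38 | 88.6% | 90.5% |
| Fieller, 0.85 | 39 | 87.3% | 89.3% |

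At CV .22, 47 per arm gives 86.9% (log) or 85.9% (Fieller) at 1.15.

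**4. The primary endpoint.** None of these power figures transfers to the change from POD1 to POD7. With equal SDs on the two days, the SD of change is SD × √(2(1 − ρ)), which exceeds the SD of the level whenever the correlation ρ is below .5. A margin of 15% of the mean change also differs from 15% of the mean level. The number needed grows with the square of (SD of change ÷ mean change), so doubling that ratio quadruples it. Neither term is given.

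**The case against.** The strongest reply is that the plan never says the margin will be computed from trial data. Section 5.4 cites external tamsulosin results that could supply a fixed value; the t-test would then be correct at .025, and 47 would be ample for the POD7 level. This stands in part: the plug-in is an inference from the absence of any fixed value, not a stated rule.

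The reply also holds that the power gap lies within the rounding of inputs given as approximate. On the log scale a CV of .24 already gives 80.9% at 47, a total of 100 would give 50 per arm, and intention-to-treat could bring in randomised non-completers beyond the 94 completers. That is fair. Extra patients do not, however, repair a wrong standard error.

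A reader might infer that the type I error is definitely inflated, or that 47 per arm is an arithmetic mistake that leaves the trial underpowered. The documents support neither. The error can move in either direction or not at all, depending on an unstated choice, and 47 agrees closely with a fixed-margin calculation.

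A separate matter may be larger. Section 5.5 says that a p-value of .05 or less "will be taken as a statistically significant result" in all cases, against .025 in section 5.4. If applied one-sided, that would double the nominal rate.

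**Conclusion.** The point holds as a specification gap with a calculable consequence. As written, the plan does not determine whether the primary test's one-sided error is about 1.7%, 2.5% or 3.4%. The outer values assume equal SDs and a margin taken from the observed tamsulosin value.

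The stated 80% power at 47 per arm is sound for a fixed margin on the POD7 level. For a valid 1.15 ratio test of that level it falls short by about 2 to 4 percentage points at CV .25. There is no shortfall at CV .22 or with a 0.85 limit. For the change endpoint that section 5.5 makes primary, no power can be stated from the documents.

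**What to change.** Before any comparison of the arms, amend sections 5.4 and 5.5 in one of two ways:

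- **Fixed margin.** State one margin as a number of USI points (for example 15% of the tamsulosin mean USI in the cited trial that supplied the CV), with the direction of benefit. Use the plain t-test against that constant. This replaces the wording in 5.5 that ties the margin to the change.
- **Percentage margin.** Name the reference arm and direction. Test the hyoscyamine mean minus 1.15 (or 0.85) times the tamsulosin mean with that contrast's own variance (Fieller). A log-scale test suits positive USI levels only, not change scores.

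In either case, say that 80% power at 47 per arm refers to the POD7 level with a fixed margin. Then restate power for the chosen test (about 76% to 78% for the 1.15 level ratio at CV .25), or show it over an assumed range of the SD of change. A fixed margin makes the t-test valid but does not by itself show that 47 is enough for the change.

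The cost is a sentence or two in each section, and a stated power that may be slightly less favourable.

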# **5.3 STUDY PROCEDURES**

To assess ureteral stent symptoms, we will be conducting the Ureteric Stent Symptoms Questionnaire (USSQ). The USSQ was created by Joshi et al as an instrument to measure stentrelated morbidity. The USSQ has been validated as a reliable instrument to measure the impact of ureteral stents. This validated questionnaire has been used in many previous studies regarding stent pain. In our study, the USSQ will be conducted prior to stent placement, on POD1, POD7 (or just prior to the time of stent removal if the removal occurs prior to day 7), and POD30. Basic demographic information, stent duration, stent size, stone location/size and obstructing vs. non-obstructing (if applicable), post stent insertion complications, drug diary information and questionnaire responses will be entered into a REDCap database for storage and analysis. The stent diameter will be 6Fr for all patients in the study. The appropriate stent length will be assigned to the patient based on cross sectional imaging. If cross sectional imaging is not available then stent length with be measured using a open-ended catheter to measure ureteral length. A small portion of these patients will be seen in the emergency department or while they are having an acute pain episode, so we expect that some of the pre-stenting questionnaires may not provide an accurate baseline for symptoms in these patients, hence the POD30 questionnaire will be obtained.

After informed consent is obtained, the patient will be prospectively randomized to either treatment arm in an open-label fashion using REDCap's randomization function to determine which therapy they will receive after stent placement. In the event that a patient does not find relief with their particular treatment arm, they will be permitted to receive additional narcotics or Pyridium. Should the patient continue to have unrelieved symptoms, treatment crossover is allowed since the study is designed in an intent-to-treat fashion.

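### The only written non-inferiority null (section 5.4) points the wrong way for a symptom score, and section 5.5 does not correct it

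*Combined protocol and SAP*

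**What the plan says.** Section 5.4 (Study design and sample size) sets the aim as showing that "hyoscyamine is not inferior to tamsulosin by more than a 15% margin in terms of the USI". It then gives the formal null: "Our null hypothesis is therefore that the mean USI for those treated with tamsulosin is more than 15% greater than those treated with hyoscyamine". The same sentence goes on to say that "by rejecting it, we may conclude hyoscyamine is not-inferior to tamsulosin by more than a 15% margin of USI".

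The outcome is the USI, one domain of the Ureteral Stent Symptom Questionnaire. Section 5.4 uses it to quantify symptoms, and section 5.3 describes the questionnaire "as an instrument to measure stentrelated morbidity". No section says outright that a higher score is worse.

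Section 5.5 (Data analysis) opens with "The main hypothesis of the non-inferiority of hyoscyamine to tamsulosin for treating lower urinary tract symptoms" and specifies a "t-test for non-inferiority of the change in USI between POD1 and POD7", or to the day of stent removal if that is earlier. It calls this test "slightly more powerful than the t-test at POD7 alone that we used to estimate the sample size". It does not restate the null, define the order of subtraction, or say which sign of the change is improvement.

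**The concern.** If a higher USI means more symptoms, the null in 5.4 says that tamsulosin is worse than hyoscyamine by more than 15%. Rejecting it shows only that tamsulosin is not that much worse. It puts no upper bound on how much worse hyoscyamine may be, which is the one thing a non-inferiority claim for hyoscyamine has to establish. The premise and the conclusion of the sentence therefore contradict each other.

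The null fixes which tail of a one-sided test is used. Read literally on the USI score, the rule would declare hyoscyamine non-inferior with high probability when it is worse, and with a probability that rises the worse it is. It would also tend to fail hyoscyamine when it is clearly better. In an open-label trial, the direction of the primary test should not have to be settled by interpretation once the data are in.

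**Working it through.** **Does 5.4 mean a score or an improvement?** The written null would point the right way if mean USI meant mean improvement. It does not. Section 5.4 speaks of the mean USI and takes its coefficients of variation (CVs, .25 and .22) from USI values at week 2 and week 1 in two cited studies. Section 5.5 confirms that sizing used POD7 alone. So 5.4 concerns score levels.

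**Inputs.** From 5.4: 47 per arm, one-sided alpha .025, nominal power 80%, CV .25 (alternative .22), margin 15%. My assumptions: tamsulosin mean set to 1, equal SDs, an additive margin of .15, and a true difference of 0 for sizing.

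**The plan's own figure.** With SD .25, margin .15 and true difference 0, the noncentral t gives 45 per arm for 80% power, and power of 82.1% at 47. The stated 47 is within 2 per arm of this. The plan does not say which scale or true ratio it used.

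**The two rules at 47 per arm.** Let d = true mean USI on hyoscyamine minus tamsulosin, so d > 0 means hyoscyamine is worse.

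- SE = .25 × √(2/47) = .0516; df = 92; t(.975) = 1.986; half-width = 1.986 × .0516 = .1024.
- Written null: rejected when the observed tamsulosin minus hyoscyamine difference is significantly below .15, that is, when observed d > −(.15 − .1024) = −.0476 (SE taken as known). Noncentrality = (.15 + d)/SE.
- Correctly directed null: rejected when observed d < +.0476. Noncentrality = (.15 − d)/SE.

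| True d | Noncentrality, written | Written null rejected | Noncentrality, correct | Correct null rejected |
|---|---|---|---|---|
| −.15 (hyoscyamine better) | 0 | 2.5% | 5.82 | 99.99% |
| 0 | 2.91 | 82.1% | 2.91 | 82.1% |
| +.05 | 3.88 | 97.0% | 1.94 | 48.4% |
| +.10 | 4.85 | 99.8% | 0.97 | 15.9% |
| +.15 (hyoscyamine worse) | 5.82 | 99.99% | 0 | 2.5% |

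A simulation of 50,000 trials per point agreed: 96.9% against 48.3% at d = +.05, and 99.99% against 2.6% at d = +.15.

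**Sensitivity.** With CV .22 (SE .0454, half-width .0901), both rules give 90.5% at equality; at d = +.15 the written null is rejected more than 99.99% of the time, against 2.5%. If 15% is read as a ratio of 1.15 with CV .25, power at equality is 76.1% (ratio of raw means, equal SDs) or 77.7% (log scale), the same in either direction. With hyoscyamine 10% worse, written against correct is 99.7% against 14.2% (raw ratio) and 99.6% against 13.7% (log). With hyoscyamine 15% worse, it is 99.99% against 2.5% (raw ratio) and 99.98% against 2.5% (log).

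**Carrying the 5.4 clause over to the change in 5.5.**

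- Change = POD1 minus POD7: a larger value is more improvement. A larger tamsulosin change means hyoscyamine did less well, so the clause points the right way.
- Change = POD7 minus POD1: a larger value is less improvement. The same clause now makes tamsulosin the worse arm, so it points the wrong way.

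A simulation with a hypothetical SD of 1 and additive margin of 0.6 (20,000 trials per point) showed this. With a true hyoscyamine deficit equal to the margin, the clause taken literally rejected 2.5% of the time under the first definition and 100% under the second. A correctly directed test made identical decisions under both.

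**The case against.** The best reply is that nobody will run the misdirected test. The clause sits in the sample-size section and describes a score-level comparison; the primary analysis in 5.5 uses the change and names the right intent. Section 5.4 itself states the right aim just before the null. An analyst would have to follow one clause against the rest of its own sentence. This stands as far as it goes: it makes a drafting slip likely and keeps the point below the most serious level. It does not remove the error, because 5.5 offers no null to put in its place.

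A second reply is that, once a higher USI is accepted as worse, a fall from POD1 to POD7 is plainly improvement, and subtraction order does not matter to a correctly directed test. That is right. The missing sign convention in 5.5 matters only because the sole null available to carry over is reversed, so it is a clarification and not a separate defect.

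A third is that "15% greater" reads more naturally as a ratio, so the additive figures do not model the exact wording. That also stands: the 82.1% power belongs to the additive reading, and power at 47 per arm falls below 80% on the ratio and log readings. But the reversal is just as large there, and power at equality is the same whichever way the null points. Reversing the clause therefore does not itself alter the sample size.

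**Conclusion.** The concern holds. Section 5.4 is wrong as written, not merely short of detail: its null and the conclusion drawn from rejecting it point in opposite directions. It should be fixed before analysis.

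At the planned 47 per arm, the written rule turns a 2.5% chance of declaring non-inferiority at a true 15% deficit into 99.99% on the additive reading, with much the same result on the ratio and log readings.

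This rests on a higher USI meaning worse symptoms, which is inferred from how 5.3 and 5.4 describe the instrument. The percentages illustrate the POD7-score test used for sizing. They are not error rates of the planned change-score test, whose SD the documents do not give.

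**What to change.** 1. In 5.4, state that a higher USI means worse symptoms, and reverse the null: mean USI on hyoscyamine exceeds mean USI on tamsulosin by 15% or more.
2. In 5.5, define improvement as USI at POD1 minus USI at POD7 (or day of stent removal). Write the null as tamsulosin's mean improvement exceeding hyoscyamine's by at least the margin.
3. In 5.5, give the decision rule: conclude non-inferiority when the upper limit of the two-sided 95% confidence interval for tamsulosin minus hyoscyamine improvement lies below the margin. For a fixed margin this is equivalent to the one-sided .025 t-test in 5.4.

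The rule needs a stated margin. The scale, reference arm and value of the 15% margin are a separate issue and are not settled by this correction.

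The cost is one reversed clause and one added sentence in 5.4, and two or three sentences in 5.5. Visits and data collection do not change, and correcting the direction leaves the planned 47 per arm as it is.

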# **5.5 DATA ANALYSIS**

The main hypothesis of the non-inferiority of hyoscyamine to tamsulosin for treating lower urinary tract symptoms will be tested using a t-test for non-inferiority of the change in USI between POD1 and POD7 (or day of stent removal if removed before day 7) in each treatment arm. This should be slightly more powerful than the t-test at POD7 alone that we used to estimate the sample size, but there are not enough data available for the distribution at POD1 in order to make a good estimate of the change. The non-inferiority margin will be 15% of the change in USI. The primary analysis will be conducted as intention-to-treat (ITT). That is, subjects will be analyzed as belonging to the arm they were randomized to, irrespective of later crossover or other modifications. This approach is in line with the current statement on Consolidated Standards of Reporting Trials (CONSORT). Descriptive statistics will be used to describe the results from all USSQ domains at each timepoint (i.e. mean and standard deviation, along with confidence intervals for urinary symptom index, pain symptom index, etc.). We will also conduct non-inferiority tests of change in score for ITT with hyoscyamine versus tamsulosin for the other domains spanned by the USSQ, including pain symptom index, general health index, work performance index, and sexual matters between POD1 and POD7, although we may not be wellpowered to detect non-inferiority for these additional domains.

The secondary goal of determining if there are differences in the amount of additional medications need to treat stent-related discomfort between treatment arms will be examined primarily through descriptive statistics. The drug diaries of all subjects will be used to tabulate the kinds and amounts of additional medications used. For each subject, the number of days that additional medications were used will be counted. The proportion of days that additional medications were used will be calculated for each group and 95% confidence intervals will be calculated.

Finally, we will also calculate the informed consent rate, and the discontinuation rate for those patients needing to be removed from the study in each arm.

In all cases, a p-value  $\leq$  .05 will be taken as a statistically significant result.

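### Section 5.5 pre-specifies no confidence interval for the arm difference in USI change and no superiority step, so a failed test has no planned reading and a claim of superiority would be post hoc

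*Combined protocol and SAP*

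**What the plan says.** The combined protocol and SAP sets the question in section 5.4: "Our hypothesis is that the hyoscyamine is at least as effective as tamsulosin in treating lower urinary tract symptoms". It frames this as non-inferiority, in the form that "hyoscyamine is not inferior to tamsulosin by more than a 15% margin in terms of the USI", sized with "an alpha-level of .025 for the one-sided t-test".

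Section 5.5 names the primary analysis. The hypothesis "will be tested using a t-test for non-inferiority of the change in USI between POD1 and POD7", or the day of stent removal if earlier, by intention to treat. There, "The non-inferiority margin will be 15% of the change in USI". The section closes by saying that a p-value of .05 or less "will be taken as a statistically significant result", without giving sidedness.

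Section 5.5 mentions intervals in two places. The first is descriptive output for the USSQ domains at each timepoint: "mean and standard deviation, along with confidence intervals for urinary symptom index, pain symptom index, etc". The second is a 95% interval per group for the proportion of days on additional medication. Neither is an interval for the arm difference in USI change. The section says nothing about testing superiority or about what is concluded if non-inferiority is not shown.

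**The concern.** A non-inferiority test on its own has two outcomes, shown or not shown. A failed test can arise because hyoscyamine is worse or because the estimate is too imprecise, and these mean different things to a prescriber. The interval for the difference tells them apart, and the plan does not commit to it. In the other direction, an interval wholly on the favourable side would support a stronger conclusion than non-inferiority. Without a stated step, that conclusion would be chosen after the data were seen.

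The timepoint summaries do not close the gap. They show the direction of any difference and allow an approximate interval for the arm difference at POD7. The primary endpoint, however, is a within-patient change. Its SD depends on the correlation between POD1 and POD7, which separate timepoint SDs do not give.

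**Working it through.** **Inputs, all from section 5.4:** CV .25, margin 15% of the mean USI, one-sided alpha .025, power 80%, 47 per arm. Assumed: normal data, equal SDs and, for the sample size, a true difference of zero. Everything is in units of the mean USI, so SD = .25 and margin = .15.

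**The plan's own figure.** Power = P(T > t(.975, 2n−2)), where T is noncentral t with 2n−2 df and noncentrality .15 / (.25·√(2/n)). The smallest n reaching 80% is 45 per arm; at n = 47 power is .821. On the log scale with limit 1.15 the figure is 50 per arm (power .777 at 47). The stated 47 is reproduced closely enough to use.

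**Expected precision.**
- SE = .25·√(2/47) = .0516
- 95% half-width = t(.975, 92)·SE = .102, or about 10% of the mean USI (9.9% at 50 per arm)
- A one-sided .05 test would correspond to a 90% interval, with half-width .086

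**Superiority power**, same noncentral t, noncentrality = true benefit / .0516:
- 15% better: 82.1%
- 10% better: 48.4%
- 5% better: 15.9%

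**How trials would be classified by a two-sided 95% interval** (simulation, 400,000 trials per row, 47 per arm):

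| True state | Non-inferiority fails | Failed, interval includes zero | Failed, interval wholly worse than zero |
|---|---|---|---|
| Equal | 18.0% | 15.6% | 2.5% |
| 10% worse | 84.3% | 35.9% | 48.4% |

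Among failed trials, the interval lies wholly on the worse side in 2.5/18.0 = 14% when the drugs are equal and in 48.4/84.3 = 57% when hyoscyamine is 10% worse. The bare test result does not report this difference.

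**Why the readings need care.** In the 10%-worse case only 0.2% of trials have an interval wholly beyond the margin. So 48.4 − 0.2 = 48.2% are wholly worse than zero and also cross the margin. A rule that calls every interval crossing the margin inconclusive would put these trials in the same class as the truly imprecise ones.

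**No alpha cost.** The unfavourable bound of a two-sided 95% interval is the one-sided .025 non-inferiority test. The non-inferiority and superiority nulls are nested, so testing superiority only after non-inferiority at the same level needs no adjustment.

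**The case against.** The strongest reply is that this is an omission of wording and not a limit of the design. The t-test and the interval are the same calculation, section 5.5 never restricts reporting to a p-value, and descriptive intervals are planned. That stands. A reader might infer that the trial will publish only a p-value, or that it is unable to show superiority or harm. The documents support neither inference; they leave the interval and its reading unstated.

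It is also fair to say that superiority is not owed. Section 1.1 speaks of equivalence and section 5.4 of being no less effective, and non-inferiority answers the latter. The superiority step is therefore an optional addition, and the 10% and 15% benefit scenarios are illustrations that the plan does not contain.

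Finally, the figures describe the USI level at a single time, while the endpoint is the change. They also ignore rescue medication and permitted crossover, which under intention to treat could shrink an observed difference. Both limits stand. What survives is that no interval for the primary contrast and no rule for a failed test are pre-specified.

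**Conclusion.** The point holds as a gap in pre-specification and should be fixed. Section 5.5 commits to a test, but not to an interval for the arm difference in USI change or to a reading of failure, and any claim of superiority would be post hoc. The planned test remains usable.

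On the level-scale illustration the gap matters. Non-inferiority fails in about 18% of trials when the drugs are equal and in about 84% when hyoscyamine is 10% worse, and only the interval helps to tell these situations apart. These figures rest on CV .25, 47 per arm, normality and equal SDs. No corresponding figures can be given for the change because its SD is not in the documents.

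**What to change.** In section 5.5, make the primary output the estimated arm difference in USI change from POD1 to POD7 with a two-sided 95% confidence interval, matching the one-sided .025 in section 5.4. State that the closing .05 threshold does not apply one-sided to this test.

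Three points must be settled first, because the interval cannot be read without them:
- **Margin.** Section 5.4 uses 15% of the USI and section 5.5 uses 15% of the change. The latter is not a fixed number as written.
- **Alpha.** Section 5.4 gives .025 one-sided; section 5.5 gives .05 with sidedness unstated.
- **Direction.** The null in section 5.4 has the tamsulosin mean more than 15% greater. If a higher USI means more symptoms (an assumption; the documents do not say), that null favours hyoscyamine. State the sign of the difference and which bound is tested.

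Then pre-state mutually exclusive readings:
- Unfavourable bound inside the margin, interval includes zero: non-inferior.
- Interval wholly on the hyoscyamine-better side of zero: non-inferior and superior. Superiority is an optional secondary claim, tested only after non-inferiority, with no alpha adjustment.
- Interval wholly worse than zero but inside the margin: non-inferior, with the difference noted.
- Interval includes both zero and the margin: inconclusive.
- Interval wholly worse than zero and crossing the margin: statistically worse, non-inferiority not shown.
- Interval wholly beyond the margin: inferior.

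The cost is an amendment to the analysis text, plus the reconciliation above, which is needed in any case. It needs no extra patients, data or alpha.
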